8.2. Secondary Immunogenicity Analyses

The secondary immunogenicity endpoints HAI and Neut seroconversion, percentage of subjects with titer >40 , and GMTs against the homologous A/H7N9 vaccine strain 21 days after the first AS03-adjuvanted 2017 H7N9 vaccination will be summarized as described above. No formal hypothesis testing is planned.

8.3. Exploratory Immunogenicity Analyses

Immunogenicity data summaries and analysis for exploratory endpoints will be presented for the PP populations.

8.3.1. Covariate Analysis

As an exploratory analysis, seroconversion and GMT of serum antibody for both HAI and Neut against the homologous 2017 A/H7N9 strain at 21 and 180 days after the second dose of AS03 adjuvanted 2017 H7N9 IIV (treatment groups 1 and 2 only) will be summarized by treatment group stratified by age (categorized as those subjects ages 19-34, 34-49, and 50-64 years) (Table 36, Table 37, Table 38, and Table 39), by sex (Table 44, Table 45, Table 46, and Table 47), by BMI (Table 52, Table 53, Table 54, and Table 55), and by prior receipt of the 2016-2017 seasonal influenza vaccine (Table 60, Table 61, Table 62, and Table 63). These analyses will be repeated for HAI and Neut titer results against each of the four IIV4 vaccine strains at 21 and 180 days post receipt of seasonal IIV4 vaccine (by age category: Table 40, Table 41, Table 42, and Table 43; by sex: Table 48, Table 49, Table 50, and Table 51; by BMI: Table 56, Table 57, Table 58, and Table 59; by prior receipt of seasonal influenza vaccine: Table 64, Table 65, Table 66, and Table 67).

The stratified summaries will be presented for the PP population. For the 2017 A/H7N9 strain it is anticipated that subjects will have little to no pre-existing antibody at baseline, so seroconversion and titer ≥ 40 endpoints will be similar.

8.3.2. Regression Modeling

Logistic and multivariate linear regression will be utilized to test for the effects of the treatment schedule on seroconversion and GMT against the homologous 2017 A/H7N9 strain and against each of the seasonal IIV4 strains for the PP population. Similar models will be fit for HAI and Neut Antibodies for each strain and time point. Separate models will be fit for data from Day 21 post dose and Day 180 post dose.

Logistic regression will be fit to examine the relationship of HAI or Neut seroconversion at 21 or 180 days after the dose of interest (second dose of AS03 adjuvanted A/H7N9 IIV for the 2017 A/H7N9 strain; IIV4 vaccination for the seasonal IIV4 strains) with treatment schedule. If the available titer data meets the required assumptions of normality after log

transformation, multiple linear regression will be fit to examine the relationship of log transformed titers at 21 or 180 days after the dose of interest (second dose of AS03 adjuvanted A/H7N9 IIV for the 2017 A/H7N9 strain; IIV4 vaccination for the seasonal IIV4 strains) with treatment schedule. All models will be fit with and without adjustment for the following covariates (Z): age in years, sex (female, male), BMI (<30 , ≥ 30), and prior receipt of seasonal influenza vaccine (did not receive 2016-2017 seasonal vaccine, received 2016-2017 seasonal vaccine). The models as shown below assume a linear relationship between age in years and both probability of seroconversion and GMT. The validity of this assumption will be assessed prior to analysis and, if the relationship between age and response is found to be non-linear, adjustments will be made to model parameters to satisfy regression assumptions. Modeling assumptions will be checked using standard diagnostic methods (e.g., using the INFLUENCE option in PROC LOGISTIC or PROC GLM). Parameter estimates and odds ratio estimates for the logistic models will be presented for the 2017 A/H7N9 strain without covariate adjustment in [Table 68](#), [Table 69](#), [Table 70](#), [Table 71](#), and with covariate adjustment in [Table 76](#), [Table 77](#), [Table 78](#), [Table 79](#); and for the seasonal IIV4 strains without covariate adjustment in [Table 72](#), [Table 73](#), [Table 74](#), [Table 75](#), and with covariate adjustment in [Table 80](#), [Table 81](#), [Table 82](#), [Table 83](#). Parameter estimates for the multiple linear regression models will be presented for the 2017 A/H7N9 strain without covariate adjustment in [Table 84](#), [Table 85](#), [Table 86](#), [Table 87](#), and with covariate adjustment in [Table 92](#), [Table 93](#), [Table 94](#), [Table 95](#); and for the seasonal IIV4 strains without covariate adjustment in [Table 88](#), [Table 89](#), [Table 90](#), [Table 91](#), and with covariate adjustment in [Table 96](#), [Table 97](#), [Table 98](#), [Table 99](#).

Model 1A: Logistic Regression (without covariate adjustment):

$$\text{logit}[P(\text{seroconversion})] = \beta_0 + \beta_1 \times \text{Treatment} + \varepsilon$$

Model 1B: Logistic Regression (with covariate adjustment):

$$\text{logit}[P(\text{seroconversion})] = \beta_0 + \beta_1 \times \text{Treatment} + \beta_2 \times Z + \varepsilon$$

Model 2A: Multiple Linear Regression (without covariate adjustment):

$$\log(\text{titer}) = \beta_0 + \beta_1 \times \text{Treatment} + \varepsilon$$

Model 2B: Multiple Linear Regression (with covariate adjustment):

$$\log(\text{titer}) = \beta_0 + \beta_1 \times \text{Treatment} + \beta_2 \times Z + \varepsilon$$

Subjects missing data for one or more covariates will be excluded from Models 1B and 2B.

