11.4.3 Sample Size

This study is planned to enroll a minimum of 60 subjects in Groups 1-2, and 30 subjects in Group 3. This study is not designed to test a formal null hypothesis. Rather, it is intended to obtain sufficient data to obtain meaningful estimates of the immune response and to uncover any safety issues that occur at a sufficiently high rate that they might be observed in a study of this size. As such, the type one error rate, alpha = 0.05, is not adjusted for multiple comparisons.

While this study is not designed to test any specific null hypothesis, the following tables illustrate the precision and power for select estimates and comparisons of interest.

[Table 3](#) indicates the probability of observing one or more safety events, such as solicited injection site or systemic reactogenicity events or an unsolicited non-serious AE of a particular type for a single treatment arm (N = 30 or 60), and for all subjects receiving AS03-adjuvanted 2017 H7N9 IIV (N = 120).

Table 3: Power (%) to Detect Safety Events:

Event Frequency	N = 30	N = 60	N = 120
≥10% Very Common	96	>99	>99
≥1%	26	45	70

Common			
$\geq 0.1\%$ Uncommon	3	6	11
$\geq 0.01\%$ Rare	<1	<1	1

Binomial confidence intervals (CI) are widest (have the least precision) when the response rate is 50%. [Table 4](#) is presented to indicate the worst-case scenario for precision of observed exact (Clopper-Pearson) binomial confidence intervals.

Table 4: Precision of Binomial Confidence Intervals:

N	95% CI
30	31-69
60	37-63
120	40-60

For each of the primary immunogenicity objective, a power analysis is provided below for testing the following hypotheses with the planned sample size, where p_c = proportion responders in comparator arm; p_e = proportion responders in experimental arm.

Test for difference in proportion responders:

$H_0: p_c - p_e = 0$ – No difference in proportion responders

$H_1: p_c - p_e \neq 0$ – difference in response rates

[Table 5](#) and [Table 6](#) present the minimum detectable differences in the proportion of subjects responding (e.g., attaining seroconversion or a titer $\geq 1:40$) between two treatment arms using a two-sided Likelihood Ratio Test and alpha = 0.05.

Primary Immunogenicity Objective 1: Evaluate antibody responses against A/H7N9 at approximately 21 days following receipt of two doses of AS03-adjuvanted 2017 H7N9 IIV. Comparison between simultaneous and sequential receipt to IIV4, i.e., Group 1 at Day 43 vs. Group 2 at Day 64.

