[Table 10](#) and [Table 11](#) illustrate the minimum detectable differences in the proportion of subjects responding (e.g., attaining seroconversion or a titer $\geq 1:40$) between two treatment groups using a two-sided Likelihood Ratio Test and $\alpha = 0.05$.

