8.1. Primary Immunogenicity Analysis

The primary immunogenicity endpoints HAI and Neut seroconversion, percentage of subjects with titer $\geq 1:40$, and GMTs against the seasonal IIV4 strains 21 days after the IIV4 vaccination for all groups and against the homologous A/H7N9 vaccine strain 21 days after the second dose of AS03 adjuvanted 2017 H7N9 IIV will be summarized as described above. The primary analysis population will be mITT, with results from the PP population providing a comparison of the sensitivity of immunogenicity results to subject adherence to protocol-

defined conditions. Regression modelling of seroconversion and log titers is planned as described in Section 8.3.2.

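### Power is stated for a difference in proportions, but the binary immunogenicity endpoints get only a logistic odds ratio for seroconversion, and titer ≥1:40 has no between-group estimate

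*SAP*

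**What the plan says.** Protocol 11.4.3 sets out a "Test for difference in proportion responders" for each primary immunogenicity objective, with null hypothesis p_c − p_e = 0. Responders are defined by example as subjects reaching seroconversion or a titer ≥1:40. Tables 5 and 6 give minimum detectable differences at 80% power, "using a two-sided Likelihood Ratio Test and alpha = 0.05". SAP section 5 repeats this for differences "between two treatment groups using a two-sided Likelihood Ratio Test", with the same figures in SAP Tables 10 and 11. Both documents add that the study is not designed to test a formal null hypothesis, and that "the type one error rate, alpha = 0.05, is not adjusted for multiple comparisons".

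On the analysis side, SAP 8.1 summarises the primary endpoints by arm and then says: "Regression modelling of seroconversion and log titers is planned as described in Section 8.3.2". Section 8.3.2 opens: "Logistic and multivariate linear regression will be utilized to test for the effects of the treatment schedule on seroconversion and GMT". It models seroconversion by logistic regression and log titer by linear regression. For the former, "Parameter estimates and odds ratio estimates for the logistic models will be presented for the 2017 A/H7N9 strain without covariate adjustment", with matching tables for the adjusted models and the IIV4 strains. The shells for Tables 68–83 have columns for parameter estimate, SE, p-value, odds ratio and 95% CI.

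Titer ≥1:40 is a primary endpoint for H7N9 and for each IIV4 strain. SAP section 8 reports it by arm with exact intervals (Tables 28–35). SAP 8.3.1 explains why it should resemble seroconversion: "For the 2017 A/H7N9 strain it is anticipated that subjects will have little to no pre-existing antibody at baseline". That remark is limited to H7N9.

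**The concern.** The trial asks whether either vaccine interferes with the response to the other. For a binary endpoint, the natural answer is how many percentage points lower the response is in one group than in another, with an interval. That is also the quantity in the power tables, but no planned output contains it. Exact intervals are per arm, and chi-square or Fisher tests appear only for solicited symptoms (Protocol 11.6.2).

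The contrast that is planned, a maximum-likelihood odds ratio, behaves poorly when nearly everyone or nearly no one responds, and it is undefined when an arm is at 0% or 100%. No fallback is stated. Titer ≥1:40 is named in the power statement but has no between-group estimate. For the four IIV4 strains nothing in the SAP says that seroconversion can stand in for it.

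**Working it through.** **Inputs.** Objective 1 compares 50 v 50. Objective 2 compares 75 (Groups 2 and 3 pooled) v 50 (Group 1). Alpha is 0.05 two-sided. Comparator rates and differences come from Protocol Tables 5 and 6. Rates beyond those tables are my assumptions, shown as a range.

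**Formulas**, for x of n and y of m responders:

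- Likelihood ratio: G² = 2[ℓ(x/n) + ℓ(y/m) − ℓ(pooled)], where ℓ is the binomial log-likelihood.
- Wald: W = [ln OR]² / [1/x + 1/(n−x) + 1/y + 1/(m−y)].
- Power: the sum of both binomial probabilities over all tables whose statistic exceeds 3.841. For Wald, a table with an arm at 0% or 100% counts as non-significant because the SE diverges.

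**Step 1: reproduce the plan, and compare Wald at the same rates.**

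| p_c v p_e | n | LRT % | Wald % |
|---|---|---|---|
| 0.50 v 0.23 | 50/50 | 81.3 | 81.0 |
| 0.60 v 0.33 | 50/50 | 79.8 | 79.8 |
| 0.70 v 0.43 | 50/50 | 80.0 | 80.0 |
| 0.80 v 0.54 | 50/50 | 80.1 | 79.3 |
| 0.90 v 0.68 | 50/50 | 80.0 | 77.0 |

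Table 5 reproduces. Table 6 (75 v 50) does too: LRT 78.8–81.6%, Wald 77.7–80.3%. The largest Wald loss in Table 5 is 80.0 − 77.0 = 3.0 points.

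**Step 2: go beyond the tabulated range (assumed rates).**

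| p_c v p_e | n | LRT % | Wald % |
|---|---|---|---|
| 0.95 v 0.76 | 50/50 | 82.6 | 70.4 |
| 0.97 v 0.80 | 50/50 | 83.8 | 53.6 |
| 0.98 v 0.80 | 50/50 | 90.8 | 46.8 |
| 0.02 v 0.20 | 50/50 | 90.8 | 46.8 |
| 0.98 v 0.80 | 75/50 | 95.1 | 69.1 |
| 0.99 v 0.85 | 75/50 | 90.8 | 38.1 |

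**Step 3: two single tables, 50 per arm.**

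- 49/50 v 40/50: OR = (49×10)/(1×40) = 12.25 and ln OR = 2.506. The variance is 1/49 + 1 + 1/40 + 1/10 = 1.145, so W = 5.48 and p = 0.019. The LRT gives p = 0.002.
- 50/50 v 40/50, one more responder: G² = 2[40 ln 0.8 + 10 ln 0.2 − 90 ln 0.9 − 10 ln 0.1] = 14.98, p = 0.0001. A fitted logistic model returns an estimate of −23, SE about 18,500 and p = 0.999. The difference in proportions is still 0.20, with score 95% CI 0.09 to 0.34.

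**Step 4: chance that at least one arm is all responders** when both true rates are p, with 50 per arm: 1 − (1 − p^50)². For p = 0.95, 0.97 and 0.98, p^50 = 0.077, 0.218 and 0.364, giving 15%, 39% and 60%.

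**Step 5: is the LRT itself the remedy?** Type I error with both rates 0.95 and 50 v 50: LRT 8.8%, Wald 0.2%, score 4.3%. The score method is nearest to nominal.

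**Step 6: the comparator for IIV4.** The shells enter Groups 2 and 3 as separate terms against Group 1. At the Table 6 differences these contrasts have Wald power of about 69–74% (v 50 in Group 2) and 37–57% (v 25 in Group 3). The pooled 75 v 50 contrast that was sized is not printed.

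**The case against.** Several points on the other side are sound.

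- The odds ratio is not the trial's only comparison. Log titer is compared by linear regression if normality holds, and GMT is a primary endpoint. When nearly everyone responds, interference may show in titers first.
- Wald is an inference from the column layout and the mention of PROC LOGISTIC. In the two-arm unadjusted model, the model likelihood ratio test would be the very test used for power, so naming the method would settle that part.
- The models sit under the exploratory heading, and the power tables are offered as illustrations in a study without a formal hypothesis.
- Titer ≥1:40 is printed side by side by arm with exact intervals, so the point difference can be read off.
- The separation chances in Step 4 assume equal true rates, so no real difference is missed in that calculation.

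Two stronger readings are therefore unsupported. A reader might infer that the planned analysis will fail. The documents give no expected rates, and inside Table 5 the loss is at most about 3 points. A reader might also infer that titer ≥1:40 goes unexamined. It is summarised; what it lacks is a contrast with an interval.

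What survives is that no planned output contains a difference in proportions with an interval, and no fallback is named for an arm at 0% or 100%. The exploratory label does not remove this, because SAP 8.1 points to these models from the primary analysis, and an estimation study needs an estimable effect.

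**Conclusion.** The concern holds as a mismatch between the stated power and the planned analysis of the binary endpoints. It is not an error in the sample size, and both power tables reproduce. Under the Wald reading, the cost in Table 5 is at most about 3 points. It is large only if true rates exceed about 95% or fall below about 5%, which the documents neither predict nor exclude; models are also fitted at 180 days. The gap for titer ≥1:40 does not depend on the Wald reading or on any assumed rate. It matters most for the IIV4 strains, where the SAP offers no reason to treat seroconversion as a substitute. The change is worth making because it is cheap and answers the interference question directly.

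**What to change.** 1. For seroconversion and titer ≥1:40, for each assay and strain at the 21-day timepoint, add the between-group difference in proportions with a score-type 95% CI (for example Miettinen–Nurminen). Use Group 1 v Group 2 for H7N9, and Group 1 v pooled Groups 2 and 3 for IIV4, as sized in Objective 2.
2. State in SAP 8.3.2 that logistic p-values and intervals use profile likelihood, with Firth penalisation when an arm is at 0% or 100%. Given the LRT's 8.8% error in Step 5, the score interval should carry the interpretation near the extremes.

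Cost: SAP wording and added rows or columns in shells, with no change to design, sample size or data collection. For titer ≥1:40 it adds 4 strains × 2 assays = 8 IIV4 comparisons and 1 × 2 = 2 for H7N9, all unadjusted. If Groups 2 and 3 stay separate, the IIV4 count is 16. Seroconversion is already modelled, although the pooled IIV4 contrast would be new there too. Changing the reactogenicity models (Tables 106–107) and back-transforming the linear models to GMT ratios are optional and not needed for this point.

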11.6.3 Immunogenicity Data

Summaries and analysis of immunogenicity data will be presented for the mITT and PP populations.

Immune responses in terms of 2017 H7N9 or IIV4 strain-specific HAI and Neut antibody titers will be summarized by treatment arm at each time point. Analyses will include number and percentage of subjects with a titer $\geq 1:40$, number and percentage of subjects achieving seroconversion (defined as either a pre-vaccination titer < 10 and a post-vaccination titer $\geq 1:40$ or a pre-vaccination titer $\geq 1:10$ and a minimum four-fold rise in post-vaccination antibody titer), and GMTs along with corresponding 95% CIs. Descriptive summary statistics will be provided for all assays and time points. The correlation between HAI and Neut antibody titers will be evaluated. Plots such as reverse cumulative distributions or longitudinal presentations of GMTs will be presented.

Additionally, the immune response, as described above, will be summarized by available covariates, such as age, sex, BMI, and prior receipt of seasonal influenza vaccine(s), and these covariates may be considered statistical modeling. As an exploratory analysis, models may be developed to evaluate the relationship between study vaccination schedule and immune response.

Additionally, N1, N2 and N9 NA-specific antibody assays are in development. If successful, N1, N2 and N9 NA-specific responses may be assessed at baseline, 21, 42, 63, and 180 days after receipt of the first study vaccination. For each time point, summaries may include number

and percentage of subjects with detectable N1, N2 and N9 NA response (to be defined in SAP based following assay development and selection) and GMTs along with corresponding 95% CIs. Descriptive summary statistics will be provided for all assays and time points. The correlation of N1, N2 and N9 NA response with HAI and Neut antibody titers will be evaluated, and plots such as reverse cumulative distributions or longitudinal presentations of GMTs will be presented.

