3.2. Endpoints

3.2.1. Primary

Safety:

- Occurrence of all serious adverse events (SAEs) following the first study vaccination through approximately 12 months after the last study vaccination.
- Occurrence of study vaccine-related SAEs following the first study vaccination through approximately 12 months after the last study vaccination.
- Occurrence of solicited injection site and systemic adverse events (AEs) following each study vaccination through 7 days after each study vaccination.
- Occurrence of clinical safety laboratory AEs following each study vaccination through approximately 7 days after each study vaccination.

Immunogenicity:

- For HAI and Neut antibodies, percentage of subjects achieving seroconversion against the 2017 H7N9 study vaccine strain (defined as either a pre-vaccination titer <1:10 and a post-vaccination titer \geq 1:40 or a pre-vaccination titer \geq 1:10 and a minimum four-fold rise in post-vaccination antibody titer) at approximately 21 days after 2 doses of AS03-adjuvanted 2017 H7N9 IIV (Group 1 – Day 43; Group 2 – Day 64; Group 3 – N/A).
- For HAI and Neut antibodies, percentage of subjects achieving seroconversion against each of the study IIV4 strains at approximately 21 days after receipt of study IIV4 (Groups 1, 2 and 3 – Day 22).
- For HAI and Neut antibodies, percentage of subjects with an antibody titer of \geq 1:40 against the influenza 2017 H7N9 study vaccine strain at approximately 21 days following receipt of 2 doses of AS03-adjuvanted 2017 H7N9 IIV (Group 1 – Day 43; Groups 2 – Day 64; Group 3 – N/A).
- For HAI and Neut antibodies, percentage of subjects with an antibody titer of \geq 1:40 against each of the study IIV4 strains at approximately 21 days after receipt of study IIV4 (Groups 1, 2 and 3 – Day 22).

- GMTs of serum HAI and Neut antibodies against the 2017 H7N9 IIV strain at approximately 21 days following receipt of 2 doses of AS03-adjuvanted 2017 H7N9 IIV (Group 1– Day 43; Group 2 – Day 64; Group 3 – N/A).
- GMTs of serum HAI and Neut antibodies against each of the 2017 IIV4 strains at approximately 21 days after receipt of IIV4 (Group 1, 2 and 3– Day 22).

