4.5.2. Immunogenicity Variables

Individual HAI and Neut results will be reported by the central immunology laboratory for the homologous 2017 A/H7N9 vaccine strain, A/Hong Kong/125/2017, the homologous strains in the seasonal 2017/2018 IIV4 Fluzone vaccine (A/Michigan/45/2015 X-275 (H1N1), A/Hong Kong/4801/2014 X263B(H3N2), B/Phuket/3073/2013 (B Yamagata lineage), and B/Brisbane/60/2008 (B Victoria lineage)). Assay results are reported as a reciprocal titer with values of $10 \cdot 2^k$, where $k=0, 1, 2$, etc. The lower limit of detection for the HAI and Neut assays is 1:10; values below the limit of detection are reported as '<10', and for analysis are imputed as one-half the limit of detection ($10/2 = 5$). For analysis, the geometric mean (calculated on natural log scale) of repeated results for each sample will be computed and used as the response for all subsequent calculations. The variation arising from multiple measurements for an individual at a single time point is not used in subsequent calculations. See Section 3.3 for definitions of derived variables for the analysis of HAI and Neut data.

The assay to determine the influenza virus N9 Neuraminidase (NA) antibody response to vaccination is under development. An addendum to the SAP will be generated to outline the planned analyses when assay development is complete.

For subjects in Group 1 (Simultaneous Administration) there is potential for an overlap between the windows for Visit 9 (Day 181 post vaccination 1 ± 14 days) and Visit 10 (Day 181 post vaccination 2 ± 14 days). Should a subject complete both visits on the same date, HAI and Neut results against the seasonal IIV4 vaccine strains on that date will be associated with Visit 9, while HAI and Neut results against the 2017 H7N9 vaccine strain on that date will be associated with Visit 10.

All immunogenicity data will be uploaded into the SDCC's electronic data capture system.

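### SAP 8.3.2 fits the log-titre models, the only planned between-group comparison of GMT, only if log titres look normal; it names no check and no fallback, and the comparison does not need the condition

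*SAP*

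**What the plan says.** SAP 3.2.1 lists among the primary endpoints "GMTs of serum HAI and Neut antibodies against the 2017 H7N9 IIV strain at approximately 21 days following receipt of 2 doses", and does the same for each IIV4 strain 21 days after IIV4. SAP 8.1, on the primary immunogenicity analysis, summarises these endpoints by group and adds: "Regression modelling of seroconversion and log titers is planned as described in Section 8.3.2".

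SAP 8.3.2 then sets a condition, "If the available titer data meets the required assumptions of normality after log", which refers to the titres once they have been log-transformed. Only where it is met does the section provide for a linear model of log titre on treatment schedule, at either time point. It gives no test, no threshold and no alternative if the condition fails. The logistic models for seroconversion in the same section carry no such condition. The assumption of linearity in age does come with a remedy, namely adjusting the model parameters.

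On the data, SAP 4.5.2 states: "Assay results are reported as a reciprocal titer with values of" 10 times a power of two. Results below 10 "for analysis are imputed as one-half the limit of detection", that is, as 5. Repeated results for a sample are combined as a geometric mean, and Listing 9 provides for two replicates.

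On status, SAP 8.3.2 falls under the exploratory heading and uses the per-protocol population, whereas SAP 8.1 makes mITT primary. Protocol 11.6.3 says: "As an exploratory analysis, models may be developed to evaluate the relationship between study vaccination schedule and immune response".

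**The concern.** The trial's stated aim includes assessing interference between the two vaccines, which is a question about differences between groups. For GMT, Models 2A and 2B are the only place where the SAP plans such a contrast. Section 8 otherwise gives GMTs and CIs group by group.

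Read literally, a failed check means the model is not fitted. Three features make that more than a drafting slip.

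- **The assay works against the check.** Values of 5, 10, 20, 40 and so on, with a pile-up at 5, are not normal, even if the underlying response is.
- **The outcome depends on the results.** Weaker responses put more titres at the floor, so the comparison is most likely to be withheld where responses are low.
- **The decision is taken many times.** Models are fitted per strain, assay and time point: 5 strains x 2 assays x 2 times = 20 sets of titres, each checked after the data are seen. The report could mix fitted and missing contrasts, and the SAP does not say what would then fill Tables 84-99.

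**Working it through.** **The plan's own figures.** Neither document gives a power figure or an SD for GMT. The nearest stated figures are the minimum detectable differences in responder proportion (protocol Table 5, SAP Table 10): 0.27, 0.27, 0.27, 0.26, 0.22 at comparator rates 0.50 to 0.90, with 50 per group, 80% power and a two-sided likelihood ratio test at 0.05. Exact enumeration gives power 0.813, 0.798, 0.800, 0.801, 0.800, so the table reproduces. It fixes the working sample size and alpha but says nothing about titres.

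**Inputs from the documents.** At least 50, 50 and 25 evaluable in Groups 1, 2 and 3 (protocol 11.4.2); alpha 0.05; grid 10 x 2^k; below 10 set to 5; replicates averaged on the log scale.

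**Assumptions not in the documents.** Normal latent log2 titre with SD 1.0, 1.5 or 2.0; latent mean titre 10 x 2^m for m = 0.5, 1.5, 2.5, 3.5, that is about 14, 28, 57 and 113; replicate SD 0.5 log2. Shapiro-Wilk at 5% on pooled within-group residuals (n = 100) stands in for the unnamed check.

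**Construction.** Each reading is y = floor(latent log2(titre/10)), with y = -1 (titre 5) when the latent value is below 0. The analysed value is the mean of two such readings. For two groups, Model 2A is the pooled comparison t = (mean1 - mean2) / [s x sqrt(1/n1 + 1/n2)].

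**Results, mean of two replicates, 50 v 50, no true difference, 4,000 trials per row**

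| log2 SD | Latent mean titre | At floor | Shapiro-Wilk fails | Type I error, model always fitted |
|---|---|---|---|---|
| 1.0 | 14 | 23% | 100% | 5.5% |
| 1.0 | 28 | 5% | 50% | 5.0% |
| 1.0 | 57 | 0% | 28% | 4.1% |
| 1.0 | 113 | 0% | 31% | 4.6% |
| 1.5 | 14 | 31% | 100% | 5.1% |
| 1.5 | 28 | 12% | 95% | 5.9% |
| 1.5 | 57 | 4% | 20% | 5.2% |
| 1.5 | 113 | 1% | 11% | 4.4% |
| 2.0 | 14 | 35% | 100% | 5.1% |
| 2.0 | 28 | 19% | 99.8% | 5.0% |
| 2.0 | 57 | 9% | 70% | 4.8% |
| 2.0 | 113 | 3% | 13% | 5.1% |

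For SD 1.5-2, failure is 11-20% with under 5% of values at the floor, and 70-100% with 9% or more. Further runs of the same kind at SD 1.5-2 took the lower end to 7%. At SD 1.0 the grid is coarse relative to the spread, and failure is 28-50% even with 5% or less at the floor.

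**Is normality needed?** Over all scenarios, single readings included, type I error of the unconditional comparison is 4.1-5.9% at 50 v 50. With 4,000 trials the simulation standard error is sqrt(0.05 x 0.95 / 4,000) = 0.0034, so most of that spread is noise. At 50 v 25 (Group 1 v Group 3 for the IIV4 strains; 8,000 trials) it is 4.5-5.2%. Coverage of the 95% CI for the difference in mean log titre, under a two-fold latent difference, is 94.4-95.5%. The type I error runs include up to 40% of titres at the floor.

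**The case against.** The strongest reply has four parts.

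**Status.** The models are exploratory and per-protocol, in a trial that disclaims formal hypothesis testing (SAP 6.8). The primary handling of GMT is descriptive, in mITT. This stands. A reader might infer that the primary GMT analysis itself can vanish. It cannot: SAP 8.1 links the models to the primary endpoints without making them the primary analysis.

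**What is lost.** Per-group GMTs with 95% CIs, reverse cumulative curves and GMT plots are unconditional. The ratio of two reported GMTs can be taken by hand, and since the groups are independent an approximate CI follows. This also stands. The loss is confined to the modelled contrast, its p-value and the covariate-adjusted version.

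**Intent.** Elsewhere SAP 8.3.2 says that all models will be fitted and their estimates presented, and seven of the shells in Tables 84-99 are starred for the preliminary report. The condition may simply be loose wording. That is possible, but it is the only sentence that governs the choice, and it gives the analyst permission to omit.

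**Size.** The SAP does not name Shapiro-Wilk. Its one example of a diagnostic is the INFLUENCE option, and a visual check would fail less often. A reader might take the failure rates as the probability that the SAP drops the analysis, or quote the higher rates for single readings. The documents support neither: the check is unspecified, and averaged replicates are what will be analysed.

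**Conclusion.** The point holds in limited form. SAP 8.3.2 makes the only modelled comparison of GMT between schedules depend on a property that these titres often lack and that the comparison does not need at 50 per group. Under an assumed Shapiro-Wilk check with log2 SD 1.5-2 and replicate SD 0.5, duplicate means fail in about 7-20% of trials with few values at the floor, and in 70-100% with about 9% or more there. The type I error of the unconditional fit stays near 5%.

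The failure rates rest on an assumed check and on assumed titre distributions. The lack of a fallback is plain from the text, and the validity of the unconditional comparison held in every scenario tried.

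A reader might also infer that robust standard errors or a censored model are required. The simulations do not show that: ordinary least squares already holds its error rate and coverage in the unadjusted comparison.

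**What to change.** In SAP 8.3.2, delete the normality condition and state that Models 2A and 2B will always be fitted on log titre for each strain, assay and time point. Report the GMT ratio with 95% CI, obtained by back-transforming the treatment coefficient and its limits, and add that column to Tables 84-99.

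If the sponsor wants protection against non-normality or many values at the floor, name a robust-standard-error, rank or censored (Tobit) analysis in advance as a sensitivity analysis. It should not decide whether the main model is reported.

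The cost is one SAP sentence and one derived column, with no extra data or visits. The change is best made before titre results are received.
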